### **9.1 STUDY DESIGN**

Data extraction from both databases (I and II, see [section 9.4](#)) will be conducted by

. All patients will be required to have a prescription for ICS/LABA therapy [e.g. Advair (Diskus and HFA), Airduo, Breo, Dulera, or Symbicort]. The date of the first prescription of ICS/LABA within the study period (Jan 1st 2016 to Nov 30th 2018) will be defined as ICS/LABA-initiation (ICS/LABAi) date. This baseline cohort will then be followed to identify two cohorts (two arms of the study). One cohort that receives a prescription for Tiotropium Respimat® 1.25 mcg (on top of baseline ICS/LABA) will be classified as the ‘Tio’ group, and the second cohort that receives a “step-up” from baseline low-dose ICS/LABA to medium/high dose ICS/LABA or from baseline medium dose ICS/LABA to high dose ICS/LABA or an additional prescription/refill of high-dose-ICS/LABA following the first prescription of baseline high dose ICS/LABA within the study period, will be classified as the ‘NonTio’ group. The date of the first prescription for Tiotropium Respimat® 1.25 mcg in the ‘Tio’ group will be defined as the index date for the ‘Tio’ group. Similarly the date of the first prescription for a “step-up” from baseline low-dose ICS/LABA to medium/high dose ICS/LABA or from baseline medium dose ICS/LABA to high dose ICS/LABA or an additional prescription/refill of high-dose-ICS/LABA following the first prescription of baseline high dose ICS/LABA (evidenced by at least 90-days of prescription utilization) within the study period will be defined as the index date for the ‘NonTio’ group.

Patients will be required to have a minimum follow-up period of 30 days after the index date for the analyses of the primary endpoint with no limit on the maximum period (this 30-day minimum follow-up period requirement will be waived in a sensitivity analysis). Subject to sample size requirements, patients will be required to have available records for at least 12 months prior to the index date to ensure no prior use of Tiotropium Respimat® and to establish baseline patient characteristics. This 12-month period prior to the index date will be defined as the pre-index period.

Figure 9.1.1 Study Design

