**Table 1: Matching Parameters**

Variable Name and Type	Description	Applicable to Study Cohort: 1=IMS, 2=EMRClaims+
ICS/LABA dose on ICS/LABAI date	The dose level of the first prescription on the ICS/LABAI date (low, medium, or high)	1 and 2
Demographics (categorical and continuous variables)	Age (10-year increments) and Gender Male/Female), Region (if available, Northeast, Midwest, South, West)	1 and 2
CCI (continuous variable)	Charlson Comorbidity Index score	1 and 2
Specific comorbidities (categorical variables)	Cardiovascular conditions, cerebrovascular diseases, hypertension, diabetes, metabolic and endocrine comorbidities, anxiety and depression, gastro-esophageal reflux disease, cancer and obesity identified using appropriate ICD codes. All above measures will be coded as binary (yes/no) variables.	1 and 2
Medications (categorical variable)	Polypharmacy level matched within a range of 2 drugs (for example, 0-2,3-5,6-8,8-10 and so on).	1 and 2
Asthma Control Status: Well Control or Poor Control (categorical variable)	‘Well Controlled’ if patient has no prescriptions for an OCS, and no asthma-related emergency department visits or hospitalizations other than the first diagnosis recorded in the data extracted (Ref: Stempel JACI 2005). Categories will include Well Controlled and Not Well Controlled.	1 and 2
Hospital admissions Outpatient visits ER visits and OCS use (categorical variables)	Poorly Controlled patients (“Not Well Controlled”) will further be matched based on the presence of asthma-related admissions, outpatient visits, and ER visits or use of OCS during the pre-index period.	1 and 2
Eosinophil levels (EMRClaims+ database only) (categorical variables)	Eosinophil level categories: <150 cells/μL, 151-300cells/μL, 301-400 cells/μL, ≥400 cells/μL (as available)	2
Asthma Control Test (ACT) results (EMRClaims+ database only) (categorical variables)	ACT score categories developed based on data distribution (as available)	2

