### **IMS Pharmetrics (IMS or Database I)**

We will establish Database 1 using medical and pharmacy claim records from IMS Pharmetrics data. Data from January 2015-2018 will be extracted, with the first patient follow-up period for tiotropium 1.25 mcg dose patients starting January 2016. This database contains administrative insurance data and enrolment information derived from approximately 150 million commercially insured and Medicare lives. This longitudinal database allows documentation and analysis of the patient journey from diagnosis to intervention and follow-up. It is nationally representative covering 90% of US hospitals and compliant with current HIPAA (Health Insurance Portability and Accountability Act) regulations.

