## 9.11 SUBJECTS

1. Patients with least one asthma diagnosis in the inpatient setting or at least two separate instances of asthma diagnosis (separated by at least 30 days) recorded in the outpatient or emergency room setting will be included (ICD 9 CM: 493.xx or ICD 10: J45-J45.999).
2. Patients will be required to be already on ICS/LABA.
3. Patients below the age of 6 years on the ICS/LABAI date will be excluded.
4. Patients will be required to have available records 12 months prior to the index date (6 months will be used if patient exclusions due to this criteria adversely affect the study sample size).
5. Patients with a diagnosis of COPD at any time during the study period will be excluded.
6. Those who are on biologics at baseline will be removed.
7. After the PSM process, unmatched patients will be excluded.

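### Table 1 can class a patient as Well Controlled despite an asthma admission or ER visit in the pre-index period, and no other matching row picks that event up

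*Combined protocol and SAP*

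**What the plan says.** Section 9.3.3, Table 1, Asthma Control Status: a patient must meet two conditions to be Well Controlled. The first concerns oral steroids and is met "if patient has no prescriptions for an OCS". The second asks for "no asthma-related emergency department visits or hospitalizations other than the first diagnosis recorded in the data extracted". The row gives no look-back window for either condition and cites a published source for the definition.

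The next row of Table 1 says that Not Well Controlled patients "will further be matched based on the presence of asthma-related admissions, outpatient visits, and ER visits or use of OCS during the pre-index period". It says nothing of the kind for Well Controlled patients.

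Section 9.11, item 1, accepts "Patients with least one asthma diagnosis in the inpatient setting" as sufficient evidence of asthma. The alternative is two outpatient or ER diagnoses at least 30 days apart. No timing relative to index is given.

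Section 9.4, for Database I: "Data from January 2015-2018 will be extracted, with the first patient follow-up period for tiotropium 1.25 mcg dose patients starting January 2016". Section 9.1 requires 12 months of records before index: "This 12-month period prior to the index date will be defined as the pre-index period". Section 9.11, item 4, adds a fallback: "6 months will be used if patient exclusions due to this criteria adversely affect the study sample size".

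Two other provisions bear on the point. Section 9.3.3 also records exacerbation rate, resource use and cost at baseline. Section 9.7.1 compares baseline measures before and after matching and adjusts the outcome regressions for whatever remains unbalanced.

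**The concern.** Section 9.12 regards channeling bias as highly likely and relies on matching on the control and severity measures of Table 1 as one of two defences. An asthma admission or ER visit in the year before index is direct evidence of poor control. Under section 9.3.2.1 the same kind of event, with a primary asthma diagnosis, counts as an exacerbation when it occurs after index.

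Table 1 removes such an event from the control flag if it happens to be the first asthma diagnosis in the extract. Which event is first depends on where the data begin, so it need not be the onset of disease. If these patients are unevenly spread between the arms, the matched groups can agree on the control flag and still differ in recent severe events.

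**Working it through.** The plan states no figure for this point, so the check is first a reading of the rules together and then an illustration of size.

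**Step 1: can one event qualify a patient and then be ignored?** Take a patient whose first asthma diagnosis in the extract is an admission during the 12 months before index, with no other asthma ER visit or admission and no OCS prescription.

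- Section 9.11, item 1: the single inpatient diagnosis satisfies the asthma criterion.
- Table 1, control status: the admission is exempt and there is no OCS prescription, so the patient is Well Controlled.
- Table 1, next row: it applies to Not Well Controlled patients only, so the admission is not matched there.
- Remaining rows of Table 1 (ICS/LABA dose, demographics, CCI, comorbidities, polypharmacy, eosinophils, ACT): none codes the admission.

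The admission therefore enters no matching row. The same holds for an ER visit that is the first recorded diagnosis, provided that the patient meets item 1 by another route.

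**Step 2: can the exempted event lie inside the pre-index period?** Yes, because the rule sets no limit. In Database I, data start in January 2015 and index dates can start in January 2016. For the earliest index dates the record before index is about as long as the 12-month pre-index period, so a first diagnosis recorded before index falls within it. For later index dates the first record may be inside or well before the period. No extraction start is given for Database II.

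**Step 3: how large could the effect be?** The documents give neither the share affected nor the excess risk, so these inputs are assumptions:

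- qT, qN: shares of matched Tio and NonTio patients with an exempted pre-index event, taken as 5–10% in one arm and 2–5% in the other;
- R: their exacerbation hazard relative to other patients, taken as 2 to 3.

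With the larger share in Tio, the approximate bias factor on the hazard ratio is

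(1 + qT(R − 1)) / (1 + qN(R − 1)).

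The effect for which the plan is powered follows from section 9.5: 0.0096/0.012 = 0.0224/0.028 = 0.80. The last column multiplies 0.80 by the factor.

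| qT / qN | R | Factor | True 0.80 seen as |
|---|---|---|---|
| 5% / 5% | 2 or 3 | 1.00 | 0.80 |
| 5% / 2% | 2 | 1.05/1.02 = 1.03 | 0.82 |
| 5% / 2% | 3 | 1.10/1.04 = 1.06 | 0.85 |
| 10% / 5% | 2 | 1.10/1.05 = 1.05 | 0.84 |
| 10% / 5% | 3 | 1.20/1.10 = 1.09 | 0.87 |
| 10% / 2% | 2 | 1.10/1.02 = 1.08 | 0.86 |
| 10% / 2% | 3 | 1.20/1.04 = 1.15 | 0.92 |

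The range is 1.00 to 1.15. If NonTio held the larger share, the factors would be the reciprocals and the error would favour Tio. The formula allows nothing for the other matched covariates or for regression adjustment, so it tends to overstate what would remain.

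**The case against.** The strongest reply has four parts, and much of it stands.

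- **The affected group is narrow.** The event must be the first recorded diagnosis, fall in the pre-index period, be the only asthma ER visit or admission, and come without an OCS prescription. Many patients treated for an exacerbation will have such a prescription. A reader might infer that the rule labels the highest-risk patients as low risk. It does not: those with repeated events or OCS prescriptions remain Not Well Controlled.

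- **The exemption has a rationale.** It appears deliberate and carries a citation, which could not be checked here. A reader might infer that a first record can never be disease onset because patients are already on ICS/LABA. That does not follow. Section 9.1 starts the cohort at the first ICS/LABA prescription in the study period and states no prior-use requirement, so some first records may be true new diagnoses. Even so, an admission shortly before index remains prognostic, and the rule does not separate the two situations.

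- **There are safeguards.** An admission dropped from the flag still appears in the baseline resource use recorded under section 9.3.3, and section 9.7.1 adjusts for imbalance that is found. This is a partial answer, because the plan does not list which characteristics are checked or what counts as unbalanced.

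- **A difference between arms is not shown.** A reader might infer that the exemption works unequally because high-dose NonTio patients can index on a refill and so have shorter records. The documents give no record lengths by arm, and both arms face the same look-back requirement. That remains conjecture.

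**Conclusion.** The gap is real on the text. A pre-index asthma admission or ER visit can be left out of the control flag and out of every other row of Table 1. The number affected is unknown and probably small.

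The bias is nil if the arms are equally affected. It reaches a factor of 1.15 only with assumed shares of 10% against 2% and an assumed hazard multiplier of 3. A reader might take some distortion as certain, but the assumed ranges include 5% in both arms, where the factor is exactly 1.00. If Tio patients are the sicker group, as section 9.12 expects, the error runs against Tio.

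This is a cheap improvement to a covariate definition. It is not evidence that the matching fails.

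**What to change.** Preferred: in Table 1, define control status over the fixed pre-index period, using the same look-back for everyone, and count any asthma-related ER visit or hospitalization in that period, including one that is the first recorded diagnosis. State the same window for OCS. The following row then needs no extension for these events, because a Well Controlled patient would have no admission, ER visit or OCS prescription in the period by definition.

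Alternative, if the cited definition is kept: enter pre-index asthma admission (yes/no) and pre-index asthma ER visit (yes/no) in the propensity model for all patients. Name both among the characteristics in the section 9.7.1 balance check, and add a sensitivity analysis without the exemption.

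Cost: a sentence or two in the protocol and a small change to code. The data are already extracted. Under the preferred option slightly more patients are coded Not Well Controlled, and the flag departs from the cited definition, which should be stated in the report.

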## **9.4 DATA SOURCES**

Two separate databases will be appended to create the analytic dataset to obtain sufficient power for the primary endpoint analysis. This approach will provide both comprehensive geographic representation from national claims, and important asthma clinical measures available through electronic medical records (EMR). Both databases have been widely published in the academic asthma literature.

As a general note, this study protocol attempts to anticipate availability of detailed data elements of the two real-world data sets listed below. Consistent with accepted research standards using retrospective administrative data, evaluation of missing data and study variables is often required to ultimately finalize the study protocol as it relates to inclusion of covariates as well as secondary outcome measures.

### **IMS Pharmetrics (IMS or Database I)**

We will establish Database 1 using medical and pharmacy claim records from IMS Pharmetrics data. Data from January 2015-2018 will be extracted, with the first patient follow-up period for tiotropium 1.25 mcg dose patients starting January 2016. This database contains administrative insurance data and enrolment information derived from approximately 150 million commercially insured and Medicare lives. This longitudinal database allows documentation and analysis of the patient journey from diagnosis to intervention and follow-up. It is nationally representative covering 90% of US hospitals and compliant with current HIPAA (Health Insurance Portability and Accountability Act) regulations.

### **EMRClaims+ (Database II)**

We will establish database II using EMRClaims+®, which will offer lung function results, Asthma Control Test (ACT) scores, as well as eosinophil counts for asthma patients in addition to administrative data. EMRClaims+® is an integrated health services database containing more than 20 million EMR across seven states in the Midwestern region of the United States. The database includes administrative insurance claims of approximately 690,000 lives linked to an overlapping healthcare provider database of EMR, including laboratory values, and provider billing files.

The above two databases will be combined for the analysis of endpoints common to both databases.

## **9.5 STUDY SIZE**

The expected number of asthma patients aged 12 years and above, without concurrent COPD, and continuous enrollment for 12 months prior to the Tiotropium Respimat® date is estimated to be approximately 2,100 to be matched to double (4200 patients) the number of NonTio patients resulting in a total N =6,300. Power calculation was conducted for the primary endpoint, time-to-first exacerbation by the end of the follow-up time. The calculation was based on detecting a significant treatment effect using Cox proportional hazard model. Estimates were obtained from the MEZZO trial comparing tiotropium 2.5 µg vs. salmeterol ([P15-01655](#)). Assuming 6.4% of patients in the control group followed

up for 5.5 months will have an exacerbation (based on the salmeterol group in the MEZZO study) and assuming a constant hazard rate, equating to an exponential rate parameter of 0.012 per month for the control group and 0.0096 per month for the Tio group, the power is calculated to be 77%. Using the Primo study, assuming 26.9% of patients in the control group followed up for 11 months will have an exacerbation (based on the Tio R 5 group in the 48-week study Primo) and assuming a constant hazard rate, equates to an exponential rate parameter of 0.028 per month in the control group and 0.0224 per month in the Tio group, the power is 98%. The Mezzo-derived power calculation likely underestimates the power since our study design includes sicker patients that required a step-up in ICS treatment (not required in the Mezzo Study). While we expect that the actual power will lie between the two estimates (assuming that the patient population is similar to the less severe Primo patients and the more severe MEZZO patients), the estimated power is greater than 77%.

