## **8. RESEARCH QUESTION AND OBJECTIVES**

To evaluate the effectiveness of add on therapy with Tiotropium Respimat® compared to increasing the dose of ICS in patients with a diagnosis of Asthma and on ICS/LABA therapy.

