## **9.9 LIMITATIONS OF THE RESEARCH METHODS**

Claims and EMR data are subject to certain limitations. The presence of a claim for a filled prescription or prescription absent a claim does not indicate that the medication was consumed or that it was taken as prescribed, and any medications filled over-the-counter or provided as samples by the physician will not be observed in the claims data. Finally, as with all claims-based analyses, study results may not be generalizable to the overall population as patients who have commercial health insurance may be different from those with non-commercial or without (commercial) health insurance. Database I underrepresents the population aged 65 years and older, which may affect external validity in the case of Medicare, Medicare Advantage or Medicaid patients. Since unmatched patients will be excluded, the results may not be generalizable to all patients. Some study measures and outcomes will include missing data and hence reduce the sample size. Not all patients in Database II will have lung function results or ACT scores, therefore, the sample size for related secondary endpoints or sub-group analyses may produce results for these analyses that are not generalizable. While duplication analyses will make double counting the same patient across both datasets negligible, it should be noted that the same patient may be present in both cohorts.

Including patients with persistent use of high-dose ICS/LABA (as opposed to an increase in ICS/LABA dose) in the NonTio group, may complicate the interpretation of the results, as patients with a deterioration in their asthma necessitating an increase in asthma medication (Tio group) will be matched to patients continuing on the same medication (high-dose ICS/LABA).

No claims regarding the effectiveness of Tio should be made on the basis of this study. This real-world evidence study lacks controls available with randomized controlled trials. Patient misclassification, missing data, objective and reliable measurement of patient outcomes, and lack of detailed information regarding subjects' clinical history or clinical status during the study timeframe may undermine the accuracy of our study results.

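### Section 9.5's claim of more than 77% power is not supported by the reasons given: the ICS step-up is not required of all patients, and both scenarios rest on one unstated hazard ratio of 0.80

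*Combined protocol and SAP*

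**What the plan says.** Section 9.5 of the combined protocol and SAP plans 2,100 Tio patients matched to 4,200 NonTio patients for time to first exacerbation. It gives two scenarios:

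- MEZZO: 6.4% of controls with an event at 5.5 months, then "0.012 per month for the control group and 0.0096 per month for the Tio group, the power is calculated to be 77" per cent.
- Primo: 26.9% of controls with an event at 11 months, then "0.028 per month in the control group and 0.0224 per month in the Tio group, the power is 98" per cent.

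The MEZZO figure is called a likely underestimate because "our study design includes sicker patients that required a step-up in ICS treatment (not required in the Mezzo Study". The next sentence expects power between the two estimates, describes Primo patients as less severe and MEZZO patients as more severe, and concludes that "the estimated power is greater than 77" per cent.

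Section 9.1 defines NonTio by a dose step-up for patients starting at low or medium dose. For those starting at high dose it accepts "an additional prescription/refill of high-dose-ICS/LABA following the first prescription of baseline high dose ICS/LABA within the study period". Tio patients are defined by the tiotropium prescription alone. Section 9.9 acknowledges that Tio patients "will be matched to patients continuing on the same medication (high-dose ICS/LABA".

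Section 8 asks about tiotropium "compared to increasing the dose of ICS in patients with a diagnosis of Asthma and on ICS/LABA therapy". Table 1 lists baseline dose among the matching parameters: "The dose level of the first prescription on the ICS/LABAI date (low, medium, or high".

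**The concern.** A power floor needs a reason why the true figure cannot be lower. The reason offered is a feature of the design that section 9.1 does not impose on everyone. The second support, that the truth lies between the two trials, conflicts with the plan's own hazards and with the sentence before it.

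The two scenarios also look like a sensitivity range but do not test the effect size. That is the input most open to doubt here: section 9.12 calls channeling of sicker patients to Tio highly likely, and any imbalance left after matching would move the HR towards 1.

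Section 7 intends the results for payers and prescribers. A reader who accepts the floor could take a non-significant result as evidence against a benefit over a dose increase. At the precision that gives 77% power, the 95% CI is the HR times or divided by exp(1.96 × 0.2231 / 2.699) = 1.18. An observed HR of 0.90 would have a CI of about 0.77 to 1.06, which excludes neither 0.80 nor 1.

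**Working it through.** **Inputs from section 9.5.** N = 4,200 NonTio and 2,100 Tio; control hazards 0.012 and 0.028 per month; Tio hazards 0.0096 and 0.0224 per month; power 77% and 98%. Alpha and sidedness are not stated, so two-sided 5% is assumed. The follow-up behind the power figures is not stated either.

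**Step 1: rates and HR.** −ln(1 − 0.064)/5.5 = 0.0120 and −ln(1 − 0.269)/11 = 0.0285, which agree with the plan's rates to rounding. 0.0096/0.012 = 0.80 and 0.0224/0.028 = 0.80. The HR is identical in both scenarios and is never written down.

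**Step 2: reproduce 77% and 98%.** Events D = 4,200(1 − exp(−λc·T)) + 2,100(1 − exp(−λt·T)). Schoenfeld power = Φ(|ln HR|·sqrt(D·2/9) − 1.96). The Wald version replaces the square root by 1/sqrt(1/Dc + 1/Dt).

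| Scenario | T (months) | Events | Schoenfeld | Wald |
|---|---|---|---|---|
| MEZZO | 5.5 | 376 | 53.2% | 49.9% |
| MEZZO | 10 | 667 | 77.5% | 74.2% |
| MEZZO | 11 | 730 | 81.1% | 78.0% |
| Primo | 10 | 1,447 | 97.9% | 97.1% |
| Primo | 11 | 1,572 | 98.6% | 98.0% |

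Both printed figures therefore reproduce with a common follow-up of about 10-11 months. The MEZZO figure does not reproduce at the 5.5 months named in its own sentence: about 50-53% two-sided, and 65% even with a one-sided 5% test (Schoenfeld).

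**Step 3: vary the HR.** Scaling from the plan's figures, k = 1.960 + 0.739 = 2.699 for 77% and 1.960 + 2.054 = 4.014 for 98%. Power(h) = Φ(k·ln h/ln 0.80 − 1.96). This carries over whatever follow-up produced the plan's figures, about 10-11 months by step 2.

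| HR | From 77% | From 98% |
|---|---|---|
| 0.80 | 77% | 98% |
| 0.85 | 50% | 83% |
| 0.90 | 25% | 47% |

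**Step 4: longer follow-up.** Section 9.1 sets no maximum. With follow-up uniform over 1-35 months (assumed; everyone matched, no disenrolment) at the MEZZO rate, events number about 1,118 at HR 0.80, and power (Wald to Schoenfeld) is 92-94%. It is 71-73% at HR 0.85 and 38-39% at HR 0.90.

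**Step 5: the dose-increase comparison.** Let s be the share of matched sets with low or medium baseline dose. The documents do not give s. Taking the same event rate at every dose level and HR 0.80, power(s) = Φ(k·sqrt(s) − 1.96).

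| s (assumed) | From 77% | From 98% |
|---|---|---|
| 90% | 73% | 97% |
| 80% | 68% | 95% |
| 50% | 48% | 81% |

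**Step 6: the text of 9.5 against itself and 9.1.** A step-up is required of low- and medium-dose NonTio patients only. If the wording means that only some patients are sicker, the effect depends on their share, which is not given. The trial labelled less severe has the higher control hazard (0.028 against 0.012). The population is placed between the two trials one sentence after being called sicker than MEZZO.

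**The case against.** The best defence is that a weak justification does not make the conclusion wrong. That stands. A reader might infer that true power is below 77%, but the documents do not support this: follow-up is open-ended, and step 4 gives 92-94% at the lower event rate and the plan's own HR.

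A reader might also infer that power for the dose-increase question is below 77% for any high-dose share above zero. That is wrong too. From the 98% figure, power stays at or above 77% until the high-dose share exceeds 1 − (2.699/4.014)² = about 55%. With 1-35 months of follow-up at the MEZZO rate, an 80% low/medium share still gives 86-88%.

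Nor can it be said that the HR comes from neither trial. Section 9.5 attributes its estimates in general terms to MEZZO, and the cited report is not available here. Only the absence of a stated basis is established. Both hazards are printed, so the HR can be recovered.

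Three further points have weight. Counting all 6,300 patients is correct for the pooled Tio versus NonTio analysis as defined. Section 9.9 already discloses the refill problem and says that no effectiveness claims should be made. Section 9.12's statement about sicker Tio patients describes the position before mitigation, and no residual size is given. These points limit the importance of the finding. They do not supply the missing support for the floor, and section 9.7 still plans no estimate restricted to patients for whom NonTio means a dose increase.

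**Conclusion.** The statement that power exceeds 77% is not supported as written. The step-up premise does not describe high-dose NonTio patients or Tio patients, the severity sentence runs against the plan's hazards, and the 77-98% range tests only the event rate. At the plan's implied follow-up and a two-sided 5% test, moving the HR from 0.80 to 0.85 lowers power to about 50% (MEZZO) or 83% (Primo).

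The pooled comparison also includes controls with no dose increase. Under the same assumptions, the comparison posed in section 8 has fewer events and less power than the pooled one. The loss depends on the dose mix, and the shares in step 5 are illustrations, not estimates.

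This is a modest correction. It concerns a relied-on power statement and one missing estimate; it does not show that the study is underpowered.

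**What to change.** In section 9.5, replace the step-up justification and the unconditional floor with power tabulated at HR 0.80, 0.85 and 0.90, over stated event rates and follow-up. State HR 0.80 as an assumption. Reconcile the Primo/MEZZO severity sentence with the two hazards.

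In section 9.7, pre-specify the time-to-first-exacerbation HR among matched patients with low or medium baseline ICS/LABA dose, where NonTio means a dose increase. Match within dose level for this estimate, because section 9.12 matches on a propensity-score caliper and does not guarantee agreement on dose. Report it beside the pooled HR, with its own expected events and power.

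Cost: text changes and one additional estimate from the same data, with no extra patients. The stated power becomes a range, the restricted estimate is less precise than the pooled one, and matching within dose level may lose some matches.
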